5.3.2 Discontinuation of Subjects from Treatment

If a subject receives a liver transplant, study treatment and all treatment-related assessments will be discontinued upon transplant. The criteria to determine when a subject becomes a candidate for liver transplantation is described in Section 5.3.2.1. The subject will continue to have subsequent planned visit assessment procedures performed.

Discontinuation of the treatment in subjects who receive a TIPS insertion will be at the discretion of the investigators. In case it is decided to discontinue the subject's treatment early, study treatment will be stopped and the subject will continue to have subsequent planned visit assessment procedures performed.

Adverse events that will determine temporary subject's discontinuation from study treatment include the following:

• Subjects developing severe bleeding, Albutein 20% infusions will be temporarily stopped until the bleeding episode is resolved. For subjects with variceal bleeding, Albutein 20% infusions will be temporarily stopped until the subject has received at least 2 banding sessions. Albutein 20% infusions will be resumed after the bleeding episode is resolved or after the subject has received at least 2 banding sessions, respectively.

Adverse events that will determine permanent subject's discontinuation from study treatment include the following:

- Anaphylactic shock or transfusion-related acute lung injury
- Severe AEs (ie, acute myocardial infarction, cerebral hemorrhage, cardiac failure, pulmonary edema, or intestinal necrosis) that precludes the continuation of the subject in the clinical study

Subjects with any one of these severe AEs will be discontinued from study treatment and all treatment-related assessments, and should continue to have subsequent planned visit assessment procedures performed.

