6.1.2 Standard Medical Treatment

Standard medical treatment will be administered within 3 days (72 hours) of screening, and following randomization, per institution standards. Several guidelines are published for the management of decompensated cirrhosis (2-5). Subjects will receive SMT (see Section 4.4.1.2) for the length of the study or as long as needed.

6.2 **Prior and Concomitant Therapy**

Prior (within 30 days prior to screening) and concomitant medications must be recorded in the eCRF and subject's source documents, including the trade or generic names of the medication, the dose, the route of administration, and the duration of the medication (frequency).

Any medication administered during the study (including any blood products) will be recorded on the eCRF and subject's source documents with the exception of anesthesia related products, fluid replacement therapies, and electrolyte supplementation. In addition, products administered at different doses on the same day to manage and maintain vital functions (eg, insulin, furosemide) will only be recorded once on the eCRF and subject's source documents with the dosage reported as pro re nata.

In the event that an AE or suspected adverse drug reaction (ADR) should occur, complete details of all concomitant medications administered will be reported to the sponsor.

Usual treatments in decompensated cirrhosis will be allowed.

Treatment with terlipressin and albumin will be allowed in both treatment groups only in subjects developing type-1 HRS according to the ICA criteria (Appendix 2).

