8.3 Extent of Exposure to Albutein 20%

For subjects randomized to SMT + Albutein 20%, all Albutein exposure details will be listed by visit.

An overall summary of exposure will present the duration of exposure (weeks), number of infusions received, number of subjects who had 4 or more missing consecutive infusions, and the total volume infused (mL). Duration of exposure is defined as [(date of last infusion – date of first infusion) + 10]/7. Interruptions, dose changes, and compliance are not considered in the calculation of duration of exposure.

Albutein infusion interruptions will be summarized by visit. Number of infusions, number and percentage of infusions with interruptions, and number and percentage of infusions with interruptions due to TEAE will be summarized.

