8.4 Treatment Compliance for Albutein 20% Administration

Treatment compliance, infusion compliance, and overall compliance will be listed and summarized for the SMT + Albutein 20% group specific to the Albutein study drug treatment. In addition, the number and percentage of subjects with Albutein compliance <80%, 80% to \leq 120%, and >120% will be presented. Infusion compliance will be calculated as (number of actual infusions / number of infusions expected or planned) *100. For subjects that complete the study, the number of infusions expected is 37. For subjects who drop out from the study early, the number of infusions expected or planned will be calculated as [(date of end of study visit – date of randomization) / 10 + 1].

Treatment compliance will be calculated as (total volume infused / total volume prepared)*100. Missing visits will be excluded in the calculation.

Overall compliance will be calculated as (treatment compliance * infusion compliance)/100.

Treatment compliance for the SMT alone group is not applicable for any Albutein study drug compliance assessments.

Effective Date	09-Sep-2024
Page	27 of 52

Number	IG1601 Statistical Analysis Plan

GRIFOLS	Bioscience Industrial Group

9 Efficacy Analysis

All efficacy listings and summaries will be based on the ITT population. In addition, the primary and secondary efficacy summaries and analyses will be repeated for the PP population.

For the purposes of defining the analysis period for each of the efficacy analysis timepoints the following will be applied:

Analysis Timepoint	Analysis Period	Cut-Off Date
1 Year	362 Days	Randomization Date + 361 Days
6 Months	182 Days	Randomization Date + 181 Days
3 Months	92 Days	Randomization Date + 91 Days

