9.2.6 Total Number of Paracenteses

For each subject, the total number of reported paracentesis procedures on treatment will be calculated and summarised by treatment group.

A paracentesis procedure occurring on treatment will be defined as any paracentesis procedure that occurred with a start date/time on or after the subject's date/time of randomization (for SMT alone group) or commencement of Albutein (for SMT+ Albutein treatment group). If time is missing and the procedure occurred on or after the date of randomization (for SMT alone group) or the date of commencement of Albutein

(for SMT+ Albutein treatment group) it will be considered to have occurred while on treatment.

The rate of occurrence of paracenteses will be analyzed using Poisson regression with adjustment for overdispersion using the Pearson statistic to estimate the scale parameter.

- Null hypothesis H_0 : The rate of occurrence of paracentesis procedures SMT + Albutein 20% is greater than or equal to the rate of occurrence of paracentesis procedures on SMT alone. [i.e. $Rate\ ratio\ (SMT+Albutein\ 20\% \ vs \ SMT\ Alone) \geq 1$].
- Alternative hypothesis H_a : The rate of occurrence of paracentesis procedures on SMT + Albutein 20% is less than the rate of occurrence of paracentesis procedures on SMT alone. [i.e. $Rate\ ratio\ (SMT+Albutein\ 20\% \ vs \ SMT\ Alone) < 1$].

The rate of occurrence of paracentesis procedures in the SMT + Albutein 20% treatment group will be compared to the rate of occurrence of paracentesis procedures in the SMT alone group. The response variable in the model will be the total number of procedures experienced by a subject while on treatment. The model will include treatment group, IWRS stratification factors of region (Europe or North America) and history of hospitalization for acute decompensation of liver cirrhosis (yes or no) as factors. The logarithm of the subjects' treatment duration will be used as an offset variable in the model to adjust for subjects having different exposure times during which the events could occur. The estimated treatment effect (i.e. the incidence rate ratio of SMT + Albutein 20% versus SMT alone) and corresponding 95% confidence interval (CI) will be presented.

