9.3.6 Number and Length of Hospital Readmission for an Acute Complication of Cirrhosis

All occurrences of hospital admissions are collected via eCRF through Month 12 and will be listed.

For each subject, the number of hospital readmissions due to acute complication of cirrhosis will be counted. This endpoint will be presented by treatment as a continuous variable and analyzed by Poisson regression with adjustment for overdispersion using the Pearson statistic to estimate the scale parameter. The total number of hospital admissions in the SMT + Albutein 20% treatment group will be compared to the SMT alone. The response variable in the model will be the total number of hospital admissions experienced by a subject while on treatment. The model will include treatment group, IWRS stratification factors of region (Europe or North America) and history of hospitalization for acute decompensation of liver cirrhosis (yes or no) as factors. The logarithm of the subjects' treatment duration will be used as an offset variable in the model to adjust for subjects having different exposure times during which the events could occur. The estimated treatment effect (ie, the incidence rate ratio of SMT + Albutein 20% versus SMT alone) and corresponding 95% confidence interval (CI) will be presented.

Hospital readmissions occurring on treatment are defined as any hospital admission that occurred with a start date/time on or after the subjects treatment start date/time (treatment start date/time is defined as; date/time of randomization (for SMT alone group) or commencement of Albutein (SMT+ Albutein treatment group) treatment). If time is missing and the incidence occurred on or after the date of randomization (for SMT alone group) or the date of commencement of Albutein (for SMT+ Albutein treatment group) treatment it will be considered to have occurred while on treatment. If the hospital readmission is on-going at the end of the study, it is also considered as occurring on treatment.

Number	BIG-CL-SP-000319		
	Version	2.0	Status
Effective Date	09-Sep-2024	Page	37 of 52
Effective			
GRIFOLS			
Bioscience Industrial Group			

In the event a hospital readmission occurs prior to treatment start date and the discharge date is after the treatment start date it will be counted as an occurrence.

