9.3.7 Number and Length of ICU Admission

For each subject, the number of hospital readmissions in which the subject was admitted to the ICU will be counted. This endpoint will be presented by treatment as a continuous variable and analyzed in the same way as hospital readmissions using Poisson regression with adjustment for over dispersion using the Pearson statistic to estimate the scale parameter.

ICU admission occurring on treatment are defined as any ICU admission that occurred with a start date/time on or after the subjects date/time of randomization (for SMT alone group) or commencement of Albutein (SMT+ Albutein treatment group) treatment. If time is missing and the incidence occurred on or after the date of randomization (for SMT alone group) or the date of commencement of Albutein (for SMT+ Albutein treatment group) treatment it will be considered to have occurred while on treatment.

In the event a ICU admission occurs prior to treatment start date, and the discharge date is after the treatment start date, it will be counted as an occurrence and the duration of this ICU admission will be calculated as [(discharge date – treatment start date) + 1].

For each subject, the total duration (days) of hospital readmission to the ICU will be calculated as the sum of the durations of each ICU admission (ICU discharge date – ICU admission date + 1). Descriptive statistics will be presented by treatment and analyzed by ANCOVA with adjustment for stratification factors. If a subject's ICU admission is considered on-going at the end of the study, the end of study completion date will be used to calculate the duration of the ICU readmission.

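### The paracentesis, readmission and ICU models count events with no end date but offset by an undefined treatment duration, so count and offset may cover different periods

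*SAP*

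**What the plan says.** **Count.** SAP 9.2.6: "A paracentesis procedure occurring on treatment will be defined as any paracentesis procedure that occurred with a start date/time on or after" randomization (SMT alone) or the start of Albutein (active arm). No end is given. SAP 9.3.6 uses the same kind of start bound for readmissions and adds: "If the hospital readmission is on-going at the end of the study, it is also considered as occurring on treatment". SAP 9.3.7 again gives ICU admissions only a start bound; they are "analyzed in the same way as hospital readmissions using Poisson regression with adjustment for over dispersion", so the offset carries over by cross-reference.

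**Offset.** In 9.2.6 and 9.3.6 the log of each subject's "treatment duration will be used as an offset variable in the model to adjust for subjects having different exposure times" during which events could occur.

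**Duration.** The only drug duration that the SAP defines is Albutein exposure in 8.3: last minus first infusion, plus 10 days, converted to weeks. It adds that "Interruptions, dose changes, and compliance are not considered in the calculation of duration of exposure". SMT has no counterpart. SAP 6.1.2 assumes SMT is already under way at randomization, and Protocol 6.1.2 gives it "for the length of the study or as long as needed".

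**After stopping Albutein.** Protocol 5.3.2 ends study treatment at transplant, at the investigator's discretion after TIPS, and after listed severe adverse events, but keeps subjects on planned visits. For TIPS: "study treatment will be stopped and the subject will continue to have subsequent planned visit assessment procedures performed".

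**Population and gating.** SAP 6.4.2 uses the ITT population for all efficacy analyses. SAP 6.5 places paracenteses sixth in the fixed sequence and refractory ascites seventh.

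**The concern.** A rate is interpretable only if its events and its person-time cover the same period. Here the event period has no stated end, and the person-time has a name but no definition.

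If treatment duration means time on Albutein, a subject who stops the drug and keeps attending visits adds events with no matching time. SMT subjects have no infusion to stop, so the excess falls mainly on the Albutein arm. It could hide a real reduction in paracenteses and, through the gate, prevent the test of refractory ascites.

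A second gap does not depend on how duration is read. SAP 6.4.1 limits the Albutein part of the Safety population to subjects who received some Albutein, so the plan allows for subjects randomized to Albutein and never infused. Such a subject has no start date for the count or the offset, and the model drops the record unless someone supplies a rule.

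**Working it through.** The plan gives no paracentesis rate, target rate ratio or Albutein stop rate, so it has no figure of its own to reproduce here. The stop fractions below are assumptions.

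**Inputs**
- Counting period: the 1-year cut-off in the SAP section 9 table is "Randomization Date + 361 Days", which is 362 days inclusive. Section 9.2.6 does not invoke it; it is used here as the practical end for a subject followed throughout.
- Completer's exposure under SAP 8.3, with the Month 12 infusion on Day 361: (361 − 1) + 10 = 370 days.
- Exposure with last infusion on Day 181: (181 − 1) + 10 = 190 days.
- Assumed: a fraction f of the Albutein arm stops at mid-year and stays on visits to the cut-off; everyone is followed for the full period; the SMT offset equals the full period.

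**One subject.** Last infusion on Day 181, visits to the cut-off: 362 / 190 = 1.9. The rate is 1.9 times the full-period rate.

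**Arm level.** With a log link and an arm term, the fitted arm rate is total events divided by total offset time (exact without the stratification factors, approximate with them). Relative to the full-period rate, the error factor is the counting period divided by the mean offset time.

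- Offset ends at the stop: 1 / (1 − 0.5f)
- Offset is SAP 8.3 exposure: 362 / [370(1 − f) + 190f]
- Offset is time in study: 1

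| f | Offset ends at stop | SAP 8.3 exposure | Time in study |
|---|---|---|---|
| 0% | 1.000 | 362/370 = 0.978 | 1 |
| 5% | 1/0.975 = 1.026 | 362/361 = 1.003 | 1 |
| 10% | 1/0.95 = 1.053 | 362/352 = 1.028 | 1 |
| 20% | 1/0.90 = 1.111 | 362/334 = 1.084 | 1 |

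The 8.3 column starts below 1 because the added 10 days give a completer 370 days for a 362-day period. It crosses 1 at f = (370 − 362) / (370 − 190) = 8/180 = 4.4%. If the stops come at Month 3 and the offset ends there, the factor is 1 / (1 − 0.75f): 1.039, 1.081 and 1.176 at 5%, 10% and 20%.

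**Effect on the test, as illustration.** Simulated with 205 per arm, 0.5 paracenteses per month, gamma variation between subjects (variance 1), follow-up with 61.5% event-free at 12 months (the mean of the planned 54% and 69%), true rate ratio 0.70, Albutein stops uniform over each subject's own follow-up, no SMT stops, Pearson scale, no stratification factors and 400 runs (Monte Carlo standard error at most 2.5 points). Matched periods give a ratio of 0.70 and power of about 87%. With the offset ending at the stop, 10%, 20% and 30% stopping give ratios of 0.74, 0.78 and 0.83 and power of about 69%, 51% and 28%.

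**The case against.** **The term may mean time in study.** The SAP says the offset adjusts for time during which events could occur, which is time at risk. The protocol describes a treatment period of up to 12 months for both arms, and SAP 8.3 uses a different term, duration of exposure. On that reading count and offset match. This stands as a limit: a reader might infer that the plan definitely divides post-stop events by on-drug time, and the documents do not support that. They leave the choice open, with the 8.3 definition nearest to hand.

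**SMT may be affected too.** Protocol 5.3.2 stops study treatment at transplant for any subject. If the SMT offset also ended there, the errors would partly offset each other, and would cancel if the same fraction stopped at the same time in both arms (for example 1.053 / 1.053 = 1). This stands; the figures above assume no SMT stops.

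**The error may be small.** With 8.3 exposure it is +0.3% at 5% stopping. Subjects who leave the study provide only transplant, survival and cause-of-death data (Protocol 7.2.1.4), so they add little or no mismatch. Larger errors need 10% to 20% who stop and stay on visits, which the documents neither state nor exclude.

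**The target could be on-treatment.** If few events follow the stop, an offset ending there comes close to the on-treatment rate. True, but then the count should end there too, and as written it does not.

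**The per-protocol repeat helps.** SAP 9.2 and 9.2.7.1 repeat each secondary analysis in the PP population, which excludes Albutein subjects with under 80% of expected doses or with 4 or more consecutive weeks missed. The mid-year stopper has 19 of 37 infusions (51%) and would be excluded. That would help expose the problem, but it does not correct the gated ITT test.

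**Conclusion.** The concern holds in a limited form. The count has no end bound, the offset has no definition in either arm, and Protocol 5.3.2 creates subjects for whom the two can differ. On the plain reading the Albutein rate is overstated by 2.6% to 11.1% (offset ending at the stop) or 0.3% to 8.4% (8.3 exposure) for 5% to 20% stopping at mid-year; with no stops, 8.3 exposure understates it by 2.2%. These ranges rest on assumed stop fractions, full follow-up and no SMT stops. On the time-in-study reading this error is nil. The never-infused subject is lost on either reading.

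A reader might infer a threat to the trial's main conclusion or a route to a false claim of benefit. Neither is supported. The survival endpoints do not use this offset. Once stopping exceeds a few percent, the bias runs mainly against Albutein. Paracentesis is tested confirmatorily only if the primary and the first five secondary tests succeed, and readmissions and ICU admissions are exploratory. The change should be made because it is cheap and because, if the sequence gets that far, this model decides the sixth endpoint and access to the seventh.

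**What to change.** In SAP 9.2.6, 9.3.6 and 9.3.7:

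- Count events in both arms from randomization to the earliest of death, the last visit at which these events are recorded, or randomization + 361 days. Use the log of that same time as the offset. Starting at randomization also keeps never-infused subjects in the ITT model.
- Do not end the window at the last contact date of SAP 6.1.4. It includes vital-status contacts after study exit, at which paracenteses and admissions are not collected.
- State one rule for time after transplant and apply it in both arms.
- Optionally add an on-treatment sensitivity analysis in which count and offset end on the same stated date.

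Cost: one derivation edited in three sections, with no new data. The downside is that the full-period count includes time off Albutein and so may dilute an on-drug effect, but that matches the ITT population.

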9.2.7 Incidence of Refractory Ascites

The number and percentage of subjects with at least one incidence of refractory ascites on treatment will be presented by treatment. Incidence of refractory ascites occurring on treatment is defined as any incidence that occurred with a start date/time on or after the subjects date/time of randomization (for SMT alone group) or commencement of Albutein (SMT+ Albutein treatment group) treatment. If time is missing and the incidence occurred on or after the date of randomization (for SMT alone group) or the date of commencement of Albutein (for SMT+ Albutein treatment group) treatment it will be considered to have occurred while on treatment.

A chi-square test will be used to assess if there is an association between treatment and incidence of refractory ascites.

Null hypothesis H_0 : $P1 = P2$

Alternative hypothesis H_a : $P1 \neq P2$

GRIFOLS	Number	IG1601	IG1601 Statistical Analysis Plan
	Version	2.0	
	Effective		
	Effective Date	09-Sep-2024	
	Page	33	of 52

where P1 is the proportion of subjects with at least one incidence of refractory ascites in the SMT + Albutein 20% treatment group and P2 is the proportion of subjects with at least one incidence of refractory ascites in the SMT alone treatment group. A two-sided chi-square test at a significance level of significance of 0.05 will be performed.

